1.5.2.11 TK-112690 Pharmacokinetics (PK)

Blood samples for PK were obtained on each patient at Pre-dose (Day 1), 5 hours (Day 1), and 24 hour (Day1) post-dose, and TK-112690 measured by LC/MSMS in the harvested plasma. Reports on the PK⁸⁶ and LC/MS/MS assay⁸⁷ are available. Except for a few scattered measurements, TK-112690 concentrations in pre-dose samples were nm. The two following **Figures** provide the mean TK-112690 concentration data observed with dose and dosing interval.

Figure 12. Bar chart showing mean concentration of TK-112690, pg/mL ± SE, for individual dosing intervals at 5 hours post 15, 30, 45 or 60 mg/kg dose of TK-112690. Analysis includes data from all patients who completed 4 doses.Interval 1=Study Week 1, Interval 2=Study Week 2, Interval 3=Study Week 3, and Interval 4=Study Week 4.

[figure not shown]
[figure not shown]

Figure 13.Bar chart showing mean concentration of TK-112690, pg/mL ± SE, for individual dosing intervals at 24 hours post 15, 30, 45 or 60 mg/kg dose of TK-112690.Analysis includesdata from all patients who completed 4 doses.Interval 1=Study Week 1, Interval 2=Study Week 2, Interval 3=Study Week 3, and Interval 4=Study Week 4.

⁸⁶ Tosk FSR-CL-2690 0015: PK/PD of TK-11290 Administrated to Cancer Patients in Clinical Study CLP-2690-0002.

⁸⁷ Tosk FSR-CL-2690-0014: Method Validation for "Determination of TK-112690 in Human Plasma by LC/MS/MS"

The TK-112690 blood level data suggests:

- Plasma concentrations increase with increasing dose.
- The increase in concentration observed with the 60 mg/kg dose is somewhat less than expected.
- Comparing the 5-hour and 24-hour data, the terminal elimination half-life appears to be somewhat longer than the approximately 4 hours observed in the Phase 1a study. The estimated terminal elimination half-life in this study is approximately 6 hours.

[figure not shown]
1.5.2.12 Biomarker (Uridine)

Uridine was also measured in the same samples used for PK measurement using a pilot LC/MS/MS assay.⁸⁸ The uridine data can be found in the same report providing the TK-112690 concentration data.⁸⁶

Uridine data from the study are provided in the Figure below.

Figure 14.Bar chart showing mean concentration of uridine, pg/mL ± SE, for individual dosing intervals at 5 hours post 15, 30, 45 or 60 mg/kg dose of TK-112690.Analysis includes data from all patients who completed 4 doses. Interval 1=Study Week 1, Interval 2=Study Week 2, Interval 3=Study Week 3, and Interval 4=Study Week 4.

⁸⁸ Tosk ATM-2690-0002: An LC/MS/MS Test Method for Uridine in Human Plasma Post Administration of TK-112690.

Compared to the 15 mg/kg dose,⁸⁹ the 30 and 45 mg/kg, bid, doses of TK-112690 provided the expected increase in uridine (TK-112690 is an inhibitor of an enzyme responsible for the clearance of uridine, uridine phosphorylase. The reason for the less than expected increase in uridine with the 60 mg/kg, bid, dose of TK-112690 is unknown.

1.5.2.13 Surrogate Markers (CD40, CD40L, TNF-α, FGF-9)

Blood samples were obtained from each patient for surrogate marker determination at, pre-dose (Day 1), and 5-hours (Day 1), 24-hour (Day1), 48-hours (Day 2) post dosing with TK-112690 as well as at equivalent times on weeks 2, 3 and 4. Complete data for the Surrogate Markers are available in a Tosk report.⁹⁰

No specific trend emerged as no dose related changes has been observed on scheduled time points in these biomarkers. This could be due to the high variability in the marker levels and few subjects per group. FGF9 measurements were almost all non-measurable.

Virtually all FGF9 concentrations were found non-measurable.

⁸⁹Pre-dose uridine measurements in the study were found very variable and unreliable likely because of a mistake in the protocol positioning the pre-dose sample one hour before the TK-112690 dose which was after treatment with the nutraceutical containing uridine monophosphate. The nutraceutical treatment would be expected to initially disturb the many components of the "uridine" biochemical system. This disturbance would not be expected to measurements taken at 5 and 24 hours post the TK-112690.

⁹⁰ Tosk FSR-CL-2690-0016: Plasma Concentrations CD40, CD40L, FGF9, and TNF-(Post TK-11290 Administration to Cancer Patients in Clinical Study CLP-2690-0002.

1.5.2.14 Mucositis Status

Patients were evaluated for mucositis status on Day 0, pre-dose (Day 1), 24 hours (Day 1), 48 hours (Day 2), at equivalent times on 2, 3, and 4 weeks post-dose. The mucositis evaluation included four standard scales: CTCAE/mucositis, WHO/Oral Mucositis, PROMS, and OMAS/Sonis.

Data for the scales are provided below. In general, the mucositis experience experienced by the patients was low, and many low values were recorded by the Scales. Much higher values would be expected in patients dosed with methotrexate but with no TK-112690.

Figure 15. Bar chart showing mean score NCI mucositis scale for individual dosing intervals at 24 and 48 hours post 15, 30, 45 or 60 mg/kg dose of TK-112690. Analysis includes data from all patients evaluated.

[figure not shown]

Figure 16. Bar chart showing mean score WHO oral mucositis scale for individual dosing intervals at 24 and 48 hours post 15, 30, 45 or 60 mg/kg dose of TK-112690. Analysis includes data from all patients evaluated.

[figure not shown]
[figure not shown]

Figure 17. Bar chart showing mean score PROMS scale for individual dosing intervals at 24 and 48 hours post 15, 30, 45 or 60 mg/kg dose of TK-112690. Analysis includes data from all patients evaluated.

CONFIDENTIAL Tosk, Inc **Figure 18**. Bar chart showing mean OMAS mouth pain score for individual dosing intervals at 24 and 48 hours post 15, 30, 45 or 60 mg/kg dose of TK-112690. Analysis includes data from all patients evaluated.

[figure not shown]
[figure not shown]

Figure 19. Bar chart showing mean OMAS difficulty swallowing score for individual dosing intervals at 24 and 48 hours post 15, 30, 45 or 60 mg/kg dose of TK-112690. Analysis includes data from all patients evaluated.

The scores in the mucositis scale tests suggest that TK-11290 at doses of 45 and 60 mg/kg, bid, mitigated mucositis produced by a relatively high methotrexate dose of 45 mg/m².

1.5.2.15 Overall Summary

The findings above from the Phase 1b study suggest:

- Although numerous adverse events, some serious including two deaths, occurred during the study, none appear associated with the TK-112690 treatment. Instead, the adverse events appear associated with the methotrexate treatment or the patient's illness. None of the adverse events appears related to the dose of TK-112690 employed. All the PIs in the study agree that none of the adverse events can be attributed to the TK-11290 treatment.
- The PK of TK-112690 in patients appears like that observed in the Phase 1a study in volunteers, except the terminal elimination half-life in patients appears slightly longer. Plasma concentrations of TK-112690 increased with increasing dose of drug, although the increase at 60 mg/kg, bid, was somewhat less than expected.
- The increase in plasma uridine compared to the lowest dose administered expected by the TK-122690 treatment was achieved with the 30 mg/k, bid, and 45 mg/kg, bid, doses but not the 60 mg/kg, bid, dose..
- The suppression of CD40 levels, a measure of immune activation, with TK-112690 doses > 15 mg/kg, bid, supports the notion that TK-112690 acts to diminish the immune response which Sponsorbelieves underlies chemotherapy-induced mucositis
- The finding that TK-112690 treatment at doses > 15 mg/kg, bid, appears to decrease two liver damage markers, GGT and alkaline phosphatase needs further clinical verification and study in animals.
- The protective effect of TK-112690 on mucositis post methotrexate observed in animal studies was confirmed in the Phase 1b study. but this confirmation needs further verification in a placebo controlled clinical trial.

1.6. PURPOSE OF STUDY

METREXASSISTTM, TK-112690 for parenteral use, is a novel, non-toxic and specific therapy to treat mucositis, a major side-effect of MTX. This study is designed primarily to establish, in a placebocontrolled trial, pilot efficacy compared to placebo and secondarily to confirm the safety and tolerability of TK-112690 when administered weekly for 4 weeks along with MTX as an intravenous infusion in subjects with local, advanced, recurrent, metastatic SCCHN.

1.7. RATIONALE FOR DOSAGE

1.7.1. TK-112690

The dose of TK-112690 to be tested in patients in this study will be 45 mg/kg, bid. This dose was found tolerable and likely efficacious in the Phase 1b study in patients with SCCHN. The drug will be given iv over one hour.

1.7.2. Placebo

Placebo would be an identical a volume of isotonic saline in 10 mL vials as used for the TK-112690 dose.

1.7.3. MTX

The dose of MTX will be 45 mg/m^2 . This dose was used in the Phase 1b study in patients with SCCHN.

1.7.4 Nutritional Supplement

TK-112690 is a uridine phosphorylase (UPase) inhibitor. Inhibition of UPase leads to increased uridine which is hypothesized to be the active protecting agent. The nutritional supplement, Fortasyn Connect[™] (Nutricia NV), contains uridine monophosphate and is being dosed to ensure that all the cancer patients have enough uridine in the body for TK-112690 to have the desired effect. In multiple preclinical studies at Tosk, uridine alone, without TK-112690, had no protective effect on MTX-induced mucositis.

1.8. CONDUCT OF TRIAL

This clinical trial will be conducted according to the current revision which has its origin in the Declaration of Helsinki (Revised 59th WMA General Assembly, Seoul, October 2008 - Appendix 1). The study will be conducted in compliance with this protocol, CFR parts 50, 56 and 3112, Good Clinical Practice (CPMP/ICH/135/95), Schedule Y of the Indian Drugs and Cosmetics Act, and designated standard operating procedures.

2.0. STUDY OBJECTIVES

2.1. PRIMARY OBJECTIVE

The primary objective of this study is to establish pilot efficacy compared to placebo for TK-112690 as an anti-mucositis agent when administered weekly for 4 weeks by iv infusion to subjects with locally advanced, residual or recurrent or metastatic SCCHN scheduled to receive MTX as chemotherapy.

2.2. SECONDARY OBJECTIVES

The secondary objective of this study is to confirm the safety and tolerability of a continuous iv infusion of TK-112690 demonstrated in the Phase 1b study in patients suffering from local, advanced, residual recurrent, metastatic SCCHN receiving sequential continuous iv infusions of TK-112690 and MTX.

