Title of the Study

A Phase 2a, Multi-center, Placebo-controlled, Randomized, Partially Blinded, Study of Infused METREXASSISTTM (Parenteral TK-112690) or MetrexassistTM Placebo Administered Along with Methotrexate Weekly for Four Consecutive Weeks to Patients with recurrent or residual SCCHN.

Principal Investigators Approximately 3

Study Centers Approximately 3

Clinical Phase

Phase 2a

Number of Subjects

The total number of individuals enrolled will be 22, 11 dosed TK-112690 and methotrexate and 11 patients dosed methotrexate and placebo. All patients will be dosed a nutritional supplement to assure adequate basal levels of uridine and uridine-related biochemicals.

Study Drug:TK-112690, an anhydrouridine inhibitor of uridine phosphorylase

Projected Subject Enrollment Duration

10 months

Objectives

Primary

Determine pilot efficacy of an iv infusion of TK-112690 to placebo as a mucositis preventive in subjects with locally advanced, residual, or recurrent or metastatic SCCHN scheduled to receive MTX as chemotherapy.

Secondary

Confirmation of the safety/tolerability of a continuous administered weekly for 4 weeks and lowering of plasma concentrations of surrogate markers of mucositis, e.g., CD40/CD40L, post TK-112690 in patients

suffering from local, advanced, residual or recurrent, metastatic SCCHN receiving sequential continuous iv infusions of TK-112690 and MTX or TK-112690 placebo and MTX.

Study Design

A Phase 2a, Multi-center, Placebo-controlled, Randomized, Partially Blinded, Study in Patients with recurrent or residual SCCHN.

Patients will receive MTX at a dose of 45 mg/m² administered weekly for **4 consecutive weeks** as an iv infusion along with a nutritional supplement containing uridine monophosphate (Fortasyn ConnectTM / SouvenaidTM, Nutricia NV) administered two hours before the MTX. One hour before the MTX treatment the patients will be administered the first infusion of the day of either TK-112690 or placebo depending on randomization infusion. Five hours after the MTX treatment the patients will be administered the second treatment of either TK-112690 or placebo depending on randomization. The TK-112690 dose will be 45 mg/kg.

- A total of 22 patients will be enrolled into one of 2 different dose groups: TK-112690 treated or placebo treated.
- Screening must be within 15 days of subject enrollment.
- Patients will remain for observation at the clinical site for a minimum of 25 hours post initial TK-112690 or placebo dose.

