- Subjects that have participated in any other investigative clinical trial in the past 4 weeks.

Dose and Dosing Regimen

The dose of METREXASSISTTM (TK-112690) will be 45 mg/kg administered parenterally over one hour in a clear, neutral, aqueous formulation (no organic chemical excipients). METREXASSISTTM will be given one hour before and 5 hours after the MTX treatment. The nutrient drink will be given one hour before METREXASSISTTM infusion. The MTX formulation will that traditionally used as standard-of-

care at a study site.

Test Product, Dose and Mode of Administration

- METREXASSISTTM (TK-112690 for Infusion) is a clear, sterile, neutral (pH=7.4), aqueous solution containing 5 mL of 100 mg/mL TK-112690.
- METREXASSISTTM is packaged as a 5 mL solution in a 10 mL flint glass vial with an elastomeric stopper held in place by an aluminum seal and flip-off cap. The concentration of TK-112690 in the solution is 100 mg/mL
- METREXASSISTTM will be administered as a continuous iv infusion over a duration of one hour in a volume of 250 mL normal saline.
- The nutrient drink, Fortasyn Connect[™] / Souvenaid[™], is commercially available as a 125 mL, 125 kcal solution. The drink is administered orally.
- The placebo is isotonic saline.

Reference Therapy or Comparator

Placebo-Isotonic saline

Follow-up

[figure not shown]
Subjects need to return at Day 1 of Week 6, which is two weeks from the last dose of the study drug.

Statistical Methods

- Safety: AEs, vital signs, physical examination data and clinical laboratory data will be analyzed using descriptive statistics with safety outcomes for patients in a dose group pooled & compared with patients in other groups.
- Mucositis: Scale data from individual doses groups will be analyzed using descriptive statistics.
- Surrogate Markers: Plasma concentration data evaluated for individual doses groups using descriptive statistics as well as compared with Surrogate marker data from the completed Phase 1bstudy.

INTRODUCTION

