1.5.2.3 Overall Safety

Administration of METREXASSISTTM plus a relatively high dose of methotrexate to the cancer patients resulted in a total of 35 treatment-emergent adverse events (TEAEs) were reported in 21 (84.0%) patients; the majority were mild to moderate in severity and resolved with or without treatment. However, all events were assessed to be not related to study drug but attributed to the disease under study and/or concomitant disease conditions. A total of 6 CTCAE Grade 3/4 were reported in 5 (20%) patients.

Treatment-emergent serious adverse events (TESAEs) were reported in 5 (20%) patients. All TESAEs were assessed to be not related to the study drug but attributed to the disease under study and/co-morbidities. A total of 4 (16.0%) patients discontinued the study due to AEs. All were cases of anemia (n=4). A total of 2 (8%) patients died due to AEs. Febrile neutropenia caused one death (n=1) and pancytopenia the other (n=1).

No actions were taken for safety reasons, and there were no protocol modifications based on safety concerns associated with the TK-112690 administration. No dose limiting toxicity (DLT) was reported in any of the patients. The observed AEs, SAEs, and deaths are described or listed in the sections below.

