10.1.1. Sample Size and Associated Power

The primary objective of this Phase 2a trial is to evaluate the pilot efficacy and the safety/tolerability of MetrexassistTM administered intravenously to subjects with cancer also receiving 45 mg/m² MTX. This is

an exploratory study and is may not be powered to demonstrate statistical significance. The sample size is based not on statistical calculations but on the outcome in the Phase 1b study where all patients received TK-112690 experienced relatively little mucositis. Without the TK-112690 considerably more mucositis is expected, perhaps enough to achieve statistical significance. At a minimum, sufficient data will be obtained to accurately power the next study with TK-112690 and MTX.

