10.3.1. Incidence of Adverse Events

Adverse events will be classified and graded according to the NCI Common Terminology Criteria for Adverse Events (CTCAE), version 3.0.

The primary safety analysis using descriptive statistics will include summaries of incidence rates, severity, and type of adverse events; summary of changes in subjects' clinical laboratory results; and summaries of the number of toxicity grades for laboratory and non-laboratory data.

Adverse events will be coded using the MedDRA adverse event dictionary. Frequency of treatment emergent adverse events will be calculated for each body system, by preferred term, by treatment group, for number of subjects and proportion reporting the event. The severity of the adverse events and the relationship to study medication will be summarized for each body system and preferred term by treatment group. Withdrawals due to adverse events will be summarized for each body system and preferred term by treatment group.

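### The trial undertakes to confirm safety, but a descriptive comparison of 11 v 11 with no confidence interval cannot do so: a doubling of grade 3/4 events usually could not be told apart from chance.

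*Combined protocol and SAP*

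**What the plan says.** **Objective.** Section 2.2 gives the secondary objective as "to confirm the safety and tolerability of a continuous iv infusion of TK-112690 demonstrated in the Phase 1b study". Section 1.6 has the study "secondarily to confirm the safety and tolerability", and the synopsis lists "Confirmation of the safety/tolerability" among the secondary objectives. Section 10.1.1 places safety in the primary objective, which it words as "to evaluate the pilot efficacy and the safety/tolerability of" the product. The same section calls the trial exploratory and says the sample size does not come from a statistical calculation.

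**Size.** Synopsis: "The total number of individuals enrolled will be 22, 11 dosed TK-112690 and methotrexate and 11 patients dosed methotrexate and placebo". Section 3.5 allows for eight further subjects on a second randomization list.

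**Analysis.** Section 10.3.1: "The primary safety analysis using descriptive statistics will include summaries of incidence rates, severity, and type of adverse events". The synopsis says safety data will be "analyzed using descriptive statistics with safety outcomes for patients in a dose group pooled & compared with patients in other groups". Sections 10.3 and 10.3.2 add counts, percentages, means and standard deviations. No section gives a confidence interval, a harm margin, an acceptable upper limit or any trial-level criterion for calling safety confirmed. The rule in section 3.1.2 on withholding treatment after grade 3 or 4 events applies to the individual subject.

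**Earlier evidence.** Section 1.5.2.3 reports for Phase 1b: "A total of 6 CTCAE Grade 3/4 were reported in 5 (20%) patients". It also reports serious events in 5 patients (20%), 4 (16%) stopping for adverse events and 2 deaths (8%). All Phase 1b patients received TK-112690 with MTX.

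**The concern.** To confirm safety is to rule out an excess of harm larger than some stated amount. The plan names no such amount and produces no statistic that could rule one out. Under this objective, the only outcome that could pass for confirmation is that the two columns of a table look alike, and with 11 patients per arm they can look alike when the true rates are far apart.

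Calling safety demonstrated in Phase 1b goes further than that study allows. Its adverse events were attributed to disease, co-morbidities or MTX without a control group to support the attribution. The present trial is therefore the first placebo-controlled evidence on whether adding TK-112690 to MTX changes toxicity, and section 10.1.1 intends its data to shape the next study. At stake is the strength of the safety statement carried forward.

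**Working it through.** The plan has no safety calculation to reproduce: alpha, power, effect size and margin are all absent. The one rate it reports checks: 5/25 = 20%. Its exact (Clopper-Pearson) 95% interval is 6.8% to 40.7%, so Phase 1b itself only just fails to exclude a true rate of 40%.

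**Inputs**
- n = 11 per arm (synopsis).
- Placebo grade 3/4 rate: not in the documents. Assumed 20%, varied from 10% to 30%. The 20% is borrowed from Phase 1b patients who all received TK-112690 plus MTX.
- Harm considered: a true doubling on TK-112690.
- Two-sided 0.05 for the test: my assumption. The plan proposes no safety test, so power serves here only to measure how far chance can mask a doubling.

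**1. Exact enumeration.** Let C ~ Bin(11, p) on placebo and T ~ Bin(11, 2p) on TK-112690, independent. Sum P(C = c) × P(T = t) over (a) all pairs with t > c and Fisher p ≤ 0.05, and (b) all pairs with t ≤ c.

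| Placebo v TK-112690 | (a) Fisher power | (b) TK-112690 shows the same or fewer | TK-112690 shows more |
|---|---|---|---|
| 10% v 20% | 2% | 36% | 64% |
| 20% v 40% | 7% | 21% | 79% |
| 30% v 60% | 16% | 11% | 89% |

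With 2/11 affected on placebo, significance requires 8/11 on TK-112690 (p = 0.030); 7/11 gives p = 0.080. If the true rates were equal at 20%, TK-112690 would still show more affected patients in 39% of trials, so a raised count by itself does not establish harm.

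**2. What equal counts would mean.** For 2/11 v 2/11, each rate is 0.182 with Wilson limits 0.051 and 0.477. The Newcombe limits for the difference are ±√[(0.182 − 0.051)² + (0.477 − 0.182)²] = ±0.32, that is, -32 to +32 percentage points.

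**3. What an observed doubling would mean.** For 2/11 v 4/11, the Newcombe interval is about -18 to +49 points.

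**4. No events at all.** The one-sided 95% upper bound for 0/11 is 1 − 0.05^(1/11) = 24%; the two-sided exact limit is 1 − 0.025^(1/11) = 28%.

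**5. Sensitivity to size.** If all eight further subjects enrol and split equally (an assumption), 15 v 15 at 20% v 40% gives Fisher power of 11%, with TK-112690 showing the same or fewer in 15% of trials. By the usual normal-approximation formula, 80% power would need 82 per arm, or 91 with continuity correction.

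**The case against.** The strongest reply is that section 10.1.1 openly calls the trial exploratory, says it may not be powered and aims at least to supply data for sizing the next study. No safety test is planned, so power figures describe an analysis nobody proposes. Section 10.3.1 already tabulates event frequency, severity, relationship and withdrawals for adverse events by treatment group, and intervals follow directly from those counts. On this view the defect is a loose verb.

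Much of that stands, and it rules out three stronger readings that a reader might infer:

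- *That a doubling would usually look like no difference.* It would not. At 20% v 40%, the planned table would show more affected patients on TK-112690 in about 79% of trials. What fails is the ability to separate that excess from chance.
- *That the report would declare safety confirmed.* No section gives such a reporting rule, and the exploratory label points the other way.
- *That earlier experience with this dose rests on about two patients.* The BMI rows of Table 9 do show 4 patients at 45 mg/kg, falling to 2 by Week 4. The same rows show 15 at the higher 60 mg/kg dose, with 10 at Week 4. At or above the present dose, 4 + 15 = 19 began and 2 + 10 = 12 contributed at Week 4.

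The objection does not remove the mismatch. An exploratory trial of this size is legitimate, but that status conflicts with a stated objective of confirming safety. Without intervals a reader cannot distinguish an excess from chance, or apparent equality from lack of information.

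**Conclusion.** The point holds as a mismatch between objective and analysis. The synopsis and sections 1.6 and 2.2 promise confirmation, and descriptive summaries at 11 v 11 cannot supply it. With a 20% placebo rate, power against a doubling of grade 3/4 events is about 7% (2% to 16% for placebo rates of 10% to 30%), and TK-112690 would show no more affected patients than placebo in 21% of trials (36% to 11%). Equal counts of 2/11 leave -32 to +32 points open.

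These figures rest on the assumed placebo rate and, for power, on a two-sided Fisher test at 0.05 used as a yardstick. The eight possible extra subjects do not change the conclusion.

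A related gap bears on the remedy. Section 10.2.1 defines the safety population as subjects receiving at least one dose of TK-112690. Read literally, this leaves no placebo group, contrary to the by-group summaries promised in the synopsis and section 10.3.1.

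**What to change.** 1. **Synopsis, 1.6 and 2.2:** replace *confirm* and *Confirmation of* with *describe, by arm* or *estimate*, and in 2.2 delete the clause saying that safety was demonstrated in Phase 1b.
2. **10.3.1:** for grade 3 or higher events, serious events and discontinuations for adverse events, report the number and percentage of patients per arm with exact 95% confidence intervals, and the TK-112690 minus placebo difference with a Newcombe or score 95% interval. State that absence of an observed difference will not be reported as confirmation of safety.
3. **10.2.1:** define the safety population as all subjects who receive at least one dose of TK-112690 or placebo, so that the comparison can be made.

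The cost is wording in five places and a few intervals computed from data already collected. No patients, visits or assessments are added. The downside for the sponsor is a less favourable safety statement, since the intervals will be wide.
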